2.0 OBJECTIVES

2.1 Primary Objective

- Evaluate whether CIP can reduce progression of critical illness among patients hospitalized for COVID-19

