5.2.7 Enrollment, Screen Failures, and Study Completion

Patients are considered enrolled from time consented to participate until designated as a screen failure or have either been discontinued from the study or completed it. A screen failure is a patient who signed informed consent, but then was determined to be ineligible or withdraws from the study. Subjects are considered to have completed the study when they are followed through day 60 or have had an adverse event or death occurred prior to day 60.

Day -1 to 0 Baseline:

- A. Subject informed consent (obtained before performing study related activities)
- B. Baseline Evaluation at screening.
 1. Demographics (Age, sex ethnicity, race)
 2. Medical history (timing of exposure to COVID-19 source patient, acute and chronic medical condition, medications, allergies.) Any medical condition arising after consent should be recorded as AE.
 3. COVID-19 symptom screen (fevers, cough, shortness of breath, diarrhea, anosmia), onset of symptoms, source of contagion
 4. Vital signs

5. COVID-19 testing (RT-PCR) from nasopharyngeal, throat, tracheal aspirate or bronchoalveolar lavage and stool (optional) samples
6. Blood typing, CBC with differential, comprehensive metabolic panel
7. Serological testing: anti-SARS CoV-2 titers
8. Immune testing samples
9. Urine or serum pregnancy test for females of childbearing potential. Results from laboratory tests obtained up to 7 days before enrollment may be used for the pregnancy test.
10. Determination of eligibility as per inclusion/exclusion criteria, age, consent, positive for COVID-19, respiratory symptoms within 72 hours of admission

DAY 0 Baseline and Infusion:

1. Study Plasma Administration: 1-2 units of plasma will be transfused over 1-2 days. Time at start and end of infusion will be recorded and vital signs will be measured immediately prior to infusion, 10-20 minutes after start of infusion, at completion of infusion and 30-60 minutes after the end of the infusion
2. COVID-19 symptom screen (fevers, cough, shortness of breath)
3. Assessment of clinical status (8-point ordinal scale)
4. New medical conditions, concomitant medication, AE evaluation
5. Physical examination
6. COVID-19 testing (RT-PCR) from nasopharyngeal, throat or stool (optional) samples
7. Blood typing, CBC with differential, comprehensive metabolic panel, C-reactive protein
8. Serological testing: anti-SARS CoV-2 titers

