7.0 STATISTICAL CONSIDERATIONS

7.1 Statistical Analyses

Twenty-nine evaluable patients will have 80% power to declare a significant decrease in ICU admissions from a historical control of 50% of hospitalized patients to 25% with a two-sided type I error of 0.05 (reject ICU admission rate=50% if only 8 or less patients are admitted to ICU among 29 evaluable patients). The historic control group will consist of 29 patients who are gender and age (within 5 years) matched.

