7.2 Expected accrual rate, accrual duration, and study duration

Our anticipated accrual rate is 6-8 patients per month. Thus, it should take approximately 3-5 months to accrue the 29 patients needed for the trial. Allowing for 28 days of follow-up to obtain the primary endpoints on the last patient enrolled and 3 months to assemble, analyze and interpret the data the total study duration is projected to be at most 18 months.

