7.3 Endpoints

7.3.1 Primary Endpoints

- Transfer to ICU
- 28 day mortality

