9.0 STATISTICAL CONSIDERATIONS

9.1 Power calculation

Twenty-nine evaluable patients will have 80% power to declare a significant decrease in ICU admissions from a historical control of 50% of hospitalized patients to 25% with a two-sided type I error of 0.05 (reject ICU admission rate=50% if only 8 or less patients are admitted to ICU among 29 evaluable patients).

Data analysis: For categorical clinical endpoints, frequency with percentage will be summarized. For the quantitative clinical variables and immune response variables measured in this objective, we will produce summary statistics (including means, medians, and standard deviations) for data at pre- and post-CIP infusions. Subsequent analyses will compare the serologic and neutralization antibody titers for anti-SARS-COV-2 antibodies and immune response variables (after a suitable data transformation to improve normal distribution, if necessary) pre- and post-treatment using a paired t-test (or Wilcoxon sign ranked test if the data are not approximately normally distributed). The level of each measured immune biomarker measured at the follow-up time points will be plotted to visually show the change of immune responses over time. To explore whether immune responses at pre- or peak improvement at post-CIP infusions associate with clinical endpoints (such as ICU admission, intubation), logistic regression for binary endpoints and Cox regression for time to event endpoints will be used to analyze each measured immune biomarker respectively. These effects will be compared to biospecimen from non-transfused immunologic controls. Analyses will adjust for other covariates such as age and co-morbidities. No

multiplicity adjustment is planned due to the nature of being exploratory. A two-sided p-value of < 0.05 will be considered significant.

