9.2 Expected accrual rate, accrual duration, and study duration

Our anticipated accrual rate is 6-8 patients per month. Thus, it should take approximately 3-5 months to accrue the 29 patients needed for the trial. Allowing for 6 months of follow-up to obtain the primary endpoint on the last patient enrolled and 3 months to assemble, analyze and interpret the data the total study duration is projected to be at most 2 years.

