10.9 Subject Status Definitions

- Enrolled: All subjects who sign an informed consent will be considered enrolled on the study. All subjects consented on the study must be entered into Clinical Trials Office Database.
- Screen Failure: A subject who is withdrawn or discontinues from study screening prior to being on study is considered a screen failure. Screen failures are not considered a study accrual and will be replaced. Note: The IRB defines any individual that has signed an informed consent as an enrollment in this study and so screen failures should be reported to the IRB with enrollment numbers.
- On-Study: A subject is considered on-study on the date when the study team has confirmed the subject has met all of the inclusion and none of the exclusion criteria, and the treating physician/surgeon or study PI has signed off on the confirmation.
- On-Treatment: A subject is considered on-treatment on the date that they receive the first study treatment. A subject who is withdrawn or discontinues from the study after receiving at least 1 infusion is considered a discontinuation and will not be replaced.
- On Follow-up: A subject is considered on follow-up on the date that they have met any of the criteria in section 4.0.
- Off-Study: A subject is considered off-study if they are removed from the study for any of the reasons listed in section 4.0 or if they have completed all study assessments through follow-up.
- Immunologic Controls: A subject for whom biospecimen is obtained from the COVID-19 Biorepository.

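### The single efficacy rule counts ICU admissions among undefined evaluable patients and does not say how a death without ICU transfer is scored

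*Combined protocol and SAP*

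**What the plan says.** Section 7.3.1 and the Summary list two primary endpoints, transfer to the ICU and "28 day mortality". The primary objective in Section 2.1 is to "Evaluate whether CIP can reduce progression of critical illness among patients hospitalized for COVID-19".

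Only one numerical efficacy rule appears. It stands in Section 7.1 and is repeated in Section 9.1: "reject ICU admission rate=50% if only 8 or less patients are admitted to ICU among 29 evaluable patients". It is said to give 80% power for a fall from 50% to 25% at a two-sided 0.05 level. Neither section defines evaluable or mentions death.

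For mortality, the text that applies is the descriptive sentence in Section 9.1: "For categorical clinical endpoints, frequency with percentage will be summarized". The Summary and Section 2.3 promise a comparison with chart-review controls but name no method.

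Two other places bear on patients who die. Section 5.2.7 treats subjects as having completed the study if they are followed through day 60 or "have had an adverse event or death occurred prior to day 60". Section 10.9 says that a subject who leaves the study "after receiving at least 1 infusion is considered a discontinuation and will not be replaced". Neither says how the ICU endpoint is scored.

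The follow-up statements differ. Section 7.2 reads "Allowing for 28 days of follow-up to obtain the primary endpoints on the last patient enrolled"; Section 9.2 reads "Allowing for 6 months of follow-up to obtain the primary endpoint on the last patient enrolled".

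**The concern.** Death on the floor prevents the event that the rule counts. If such a patient stays among the 29, the ICU count falls by one possible admission and the rule becomes easier to meet. Within that count, a floor death and a recovery look the same. Meeting the rule would then show a lower ICU rate, but not necessarily less progression of critical illness.

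Because the scoring is unstated, it could be settled after outcomes are known. At least three scorings are open: non-admission, failure, or not evaluable. They can give different verdicts on the same data. The two follow-up statements add a second uncertainty, since they leave unclear how long after infusion an ICU transfer still counts.

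**Working it through.** **Inputs from Sections 7.1 and 9.1:** n = 29, reference ICU rate 0.50, target 0.25, two-sided 0.05, success if X ≤ 8. The floor-death rate f is not given anywhere, so every value of f below is an assumption.

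**1. The plan's own figure.** By the normal approximation, n = [1.96·√(0.5·0.5) + 0.8416·√(0.25·0.75)]² / 0.25² = 28.92, so 29, with power 80.1%. The stated 80% is reproduced.

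**2. The printed rule, exactly.** With X ~ Binomial(29, p):
- P(X ≤ 8 | 0.50) = 0.0121; doubled, 0.0241. The test is valid for the ICU rate.
- P(X ≤ 8 | 0.25) = 0.713. Exact power of the printed cutoff is 71%.
- A cutoff of 9 would have power 83.4%, but a lower tail of 0.0307 (doubled, 0.0614), so 8 is the largest cutoff that holds the level.

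**3. Floor deaths that displace ICU transfers.** Suppose ICU-or-death is truly 50% and f of it is floor death scored as non-admission. The ICU rate is 0.50 − f, and the chance of meeting the rule is P(X ≤ 8 | 0.50 − f):

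| f | Chance of meeting the rule |
|---|---|
| 0 | 1.2% |
| 2% | 2.1% |
| 3% | 2.7% |
| 5% | 4.3% |
| 10% | 11.9% |

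The value reaches 2.5% at f = 2.8 points.

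**4. Floor deaths scored as failures, cutoff kept at 8.** With an ICU rate of 25%, the failure rate is 0.25 + f:

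| f | Failure rate | P(X ≤ 8) | Loss from 71.3% |
|---|---|---|---|
| 3% | 28% | 57.4% | 14 points |
| 5% | 30% | 47.9% | 23 points |
| 10% | 35% | 26.5% | 45 points |

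The last column is also the share of trials whose verdict turns on the scoring: at most 8 ICU admissions, but more than 8 once deaths are added. It applies only with the cutoff kept at 8. With cutoffs recalculated for assumed composite references of 53%, 55% and 60% (9, 10 and 11), 4.4%, 3.8% and 9.1% of trials pass on ICU count and fail on the composite. Another 5.4%, 9.6% and 8.4% go the other way.

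**5. Floor deaths dropped as not evaluable, cutoff kept at 8.** The lower tail at 0.50 is 1.8% with 28 patients, 2.6% with 27 and 3.8% with 26.

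**6. Mortality as an estimate.** For example, 3/29 is 10%, with exact (Clopper-Pearson) 95% CI 2% to 27%.

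**The case against.** The strongest reply is that the plan does not set deaths aside. Mortality at 28 days is a listed primary endpoint, Section 8.1 adds 60-day mortality, the 8-point clinical scale is a secondary endpoint, and death is a serious adverse event reviewed by the monitoring bodies. The ICU test does what it claims. Floor deaths may be rare, and counting them as failures costs power. All of this stands. What remains is that separate reporting does not say how a floor death enters the one rule that decides the result.

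A reader might infer three stronger things that the documents do not support:
- **The rule has an inflated type I error.** The 2.7% to 11.9% figures are not error rates of the stated test. They need a 50% composite reference that the plan does not contain, together with displacement. At an ICU rate of 50% the rule succeeds 1.2% of the time whatever the floor-death rate.
- **Mortality needs its own test and threshold.** Descriptive mortality is defensible in a single-arm phase II trial. With 29 patients and a lower tail of 0.025, no rule exists at an assumed null of 5% or 10%, since even zero deaths has probability 22.6% or 4.7%. At nulls of 15% to 30%, power to detect a halving is 10% to 35%.
- **The plan directs that floor deaths count as successes.** It does not. That is what literal application of the rule gives. The wording in Section 10.9 concerns replacement, not evaluability.

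**Conclusion.** The point holds as a gap between the decision rule and the objective, not as a fault in the ICU test. Evaluable is undefined, deaths without ICU transfer are unassigned, and the literal reading favours success.

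The size cannot be fixed from the documents because they give no floor-death rate. Below about 3 points of displacement the effect on the chance of success is small. At an assumed 25% ICU rate with 3%, 5% or 10% floor deaths, the verdict would differ between the two scorings in 14%, 23% or 45% of trials, but only with the cutoff kept at 8. It should be corrected before treated outcomes are analysed, because the change is cheap and removes a choice that could otherwise be made with the results in view.

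**What to change.** - Define evaluable as all infused patients, including those who die.
- In the primary rule, count ICU transfer or death from any cause by day 28 as failure.
- Keep 50% and 8 of 29 as a conservative rule. Replace the stated 80% with exact power: 71% at a 25% failure rate, 57% at 28%, 48% at 30%.
- Report ICU transfer alone and 28-day mortality as components, mortality with an exact 95% CI.
- Reconcile Sections 7.2 and 9.2 on the follow-up for the primary endpoint.

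**Cost.** This is wording plus a restated power figure. ICU outcomes and 28-day mortality are already listed for collection in the Summary, and follow-up in Section 5.2.7 records whether treated patients are alive. The downside is lower power if floor deaths add to the ICU rate. The rule stays conservative: if the true composite rate is 53% or 55%, it succeeds 0.5% or 0.3% of the time. Setting a new composite reference would recover power, but it needs a rate that the documents do not give.

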2. Age \geq 18 years of age
3. No receipt of convalescent plasma

Immunologic Controls:

1. PBMCs with 5-10 million cryopreserved cells per specimen present in the prospective COVID 19 Biorepository
2. Serum or plasma 500 UI each from up to 50 patients present in the COVID-19 Biorepository

Assessment and Data Acquisition:

1. Baseline: Age, sex, comorbidities, date of symptom onset, known COVID-19 contact, type of admission to the floor or ICU, APACHE score (ICU scoring system to classify disease severity and mortality risk), SOFA score (mortality prediction score based on organ function), clinical status, vital signs including temperature, respiratory rate, oxygen saturation, oxygen requirement, neutrophil count, lymphocyte count, CRP, chest x-ray, chest CT, location in hospital.
2. Safety and efficacy: Day 0 (baseline), 1, 2, 3, 4, 7, 14, 21, and 28 and once at day 60.
3. SARS-CoV-2 PCR from OP or NP swabs: Day 0, 4, 7, 14 and at any time when there is clinical suspicion for COVID-19.
4. Outcome measures: increased O₂ requirement (PaO₂/FiO₂ ratio or SpO₂/FIo₂), supplemental oxygen strategy (nasal cannula, high flow nasal cannula, noninvasive ventilation, intubation and invasive mechanical ventilation, rescue ventilation i.e. neuromuscular blocking agents, prone positioning, corticosteroids, ECMO), vasopressors, renal support, ICU LOS, ICU mortality, hospital LOS, hospital mortality, 28 day mortality.
5. Serum or plasma antibody titer² to SARS-CoV-2: Day 0, 7, 14, and 28. Samples from the COVID-19 Biorepository from non-transfused patients will be assayed at two similar timepoints as Immunologic Controls.
6. Blood for immune evaluations of cellular and humoral immunity before CIP infusion (day 0) and 7, 14 and 28 days after CIP infusion. Immune testing may be done at any time if the PI determines there is a need to evaluate acute immune responses (cytokines/chemokines levels). Samples from the Prospective COVID-19 Biorepository from non-transfused patients will be assayed at two similar timepoints as Immunologic Controls.
7. "Clinical controls" will have all relevant datapoints collected via chart review (i.e. biospecimens will not be collected prospectively)

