2.3 Study Design

This is a single arm phase II trial to assess preliminary efficacy and confirm safety of infusions of anti-SARS-CoV-2 convalescent plasma in hospitalized patients with acute respiratory symptoms **with or without** confirmed interstitial COVID-19 pneumonia by CXR or chest CT. A total of 29 eligible subjects will be enrolled to receive high titer anti-SARS-CoV-2 plasma. Participants will be compared to a historical control group via retrospective chart review.

In addition, the following Immunologic Controls will be used to meet secondary objectives described above:

1. PBMCs with 5-10 million cryopreserved cells per specimen will be obtained from the prospective COVID 19 Biorepository (2 timepoints per patient t (60 specimens total) and assessed for cellular and humoral immune responses.
2. Serum or plasma 500 UI each from up to 50 patients in the Covid-19 Biorepository will be collected (2 timepoints from each patient) (100 total specimens) will be evaluated for antibody and cytokine responses.

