3.2 Experience with the use of convalescent immune plasma against coronavirus diseases

In the 21st century, there were two coronavirus epidemics associated with high mortality. The SARS outbreak in 2003 and MERS outbreak in 2012 had high mortalities and absence of effective therapies which led to the use of convalescent immune plasma. The largest study with SARS using convalescent immune plasma involved the treatment of 80 patients in Hong Kong⁷. **Patients treated before day 14 after onset of symptoms had an improved prognosis as measured by discharge from hospital before day 22.** Furthermore, those who were RT-PCR positive and seronegative for coronavirus at the time of therapy had improved prognosis. Three seriously ill patients recovered from SARS in Taiwan were treated with 500 ml of convalescent plasma which led to a reduction in plasma virus titer⁸. Three patients with MERS in South Korea were treated with convalescent plasma, but only two of the recipients had neutralizing antibody in their plasma⁹. The results suggests that providing passive antibodies may suppress the development of high titers of neutralizing antibodies to the pathogen¹⁰. The analysis of 99 samples of convalescent sera from patients with MERS showed that 87 had neutralizing antibody with a geometric mean titer of 1:61. These data suggest that antibody declines with time and/or that few patients make high titer responses. There are reports that convalescent plasma was used for therapy of patients with COVID-19 in China during the current outbreak. Although few details are available from the Chinese experience and published studies involved small numbers of patients, the available information suggests that convalescent plasma administration reduces viral load and was safe. Because of these early suggestions of benefit, it is ethically complex to conduct a placebo-controlled trial, therefore we propose to use a comparator group of patients who have been treated at UVA Medical Center prior to the start of this trial.

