4.3 Control Group (obtained via chart review and includes control specimens)

Inclusion Criteria:

1. Admitted to a “floor” bed (non-ICU bed) at UVAMC on/after March 30, 2020 due to confirmed COVID-19 disease
2. Age \geq 18 years of age

Exclusion Criteria:

1. Requiring mechanical ventilation or >6 liters per minute nasal cannula upon admission
2. Participation in other interventional anti-COVID-19 treatment trials
3. Medical conditions for which receipt of 200-400mL of intravenous fluid may be dangerous to the subject (e.g. decompensated congestive heart failure)
4. Receipt of convalescent immune plasma for treatment of COVID-19

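### Section 7.1 caps the chart-review controls at 29 but gives no rule for choosing among eligible matches and no step keeping that choice blind to ICU transfer and death

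*Combined protocol and SAP*

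**What the plan says.** Section 2.3 makes the comparison with controls part of the design: "Participants will be compared to a historical control group via retrospective chart review". The Summary says the same of outcomes, and adds that clinical controls "will have all relevant datapoints collected via chart review".

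Section 7.1 sets the size and the matching: "The historic control group will consist of 29 patients who are gender and age (within 5 years) matched". Section 4.3 filters the pool first. Controls must be adults admitted to a non-ICU bed "at UVAMC on/after March 30, 2020 due to confirmed COVID-19 disease". Excluded are patients on ventilation or more than 6 L/min nasal cannula oxygen at admission, participants in other interventional COVID-19 treatment trials, patients for whom the fluid volume may be dangerous, and recipients of convalescent plasma. Section 4.3 gives no closing date. Section 3.2 describes the group differently: "we propose to use a comparator group of patients who have been treated at UVA Medical Center prior to the start of this trial".

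The primary endpoints in Section 7.3.1 are transfer to ICU and 28-day mortality. The powered test in Sections 7.1 and 9.1 concerns ICU admission only, and its rule is to "reject ICU admission rate=50% if only 8 or less patients are admitted to ICU among 29 evaluable patients".

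The documents give no matching algorithm, no order or random rule among several fits, no masking of the person selecting, no date for locking the control list, and no use for eligible patients beyond 29. They name no test for the matched comparison.

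**The concern.** The source used to find a control also holds that patient's ICU transfer and survival. Where two or more charts fit a recipient on sex and age, someone must pick one, and the plan neither fixes the choice nor hides the outcome. Two features widen the room for choice. The admission window has no end date, and the fluid-risk exclusion is a judgement made from the chart.

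At stake is the control rate on both primary endpoints. For 28-day mortality this matters most, because the plan gives no benchmark rate and these 29 patients are the only stated comparator. Blindness to outcome cannot be demonstrated afterwards, so it has to be written in before selection.

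A lesser matter is precision. A fixed 29 leaves any further eligible patients unused, although their data could be abstracted from the same kind of chart.

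**Working it through.** **Inputs from the documents (Sections 7.1 and 9.1).** 29 evaluable recipients, 29 controls, ICU rates of 50% and 25%, two-sided alpha 0.05, power 80%.

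**Assumed inputs.** Control pools of 58, 87 and 116, since the pool size is not given. For the steering illustration, a true ICU rate of 40% in both groups and selection odds ratios of 1.25, 1.5 and 2.

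**Step 1: the plan's own figure.** For a one-sample proportion, with the null variance for alpha and the alternative variance for power:

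n = [(1.96 × √(0.5 × 0.5) + 0.8416 × √(0.25 × 0.75)) / 0.25]² = [(0.980 + 0.364) / 0.25]² = 28.9, rounded up to 29. Power at 29 is 80.1%.

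The figure reproduces under the normal approximation. (The printed cut-off of 8 has exact power 71.3%, which is a separate matter.) The calculation and the decision rule use only the count among recipients and the constant 50%. No control patient enters either, so the choice of controls cannot change that decision.

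**Step 2: precision of the comparison with controls.** At 25% in 29 recipients and 50% in m controls:

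half-width = 1.96 × √(0.1875/29 + 0.25/m)

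| Controls m | SE | 95% half-width |
|---|---|---|
| 29 | 0.123 | 24.1 points |
| 58 | 0.104 | 20.3 points |
| 87 | 0.097 | 18.9 points |
| 116 | 0.093 | 18.2 points |
| no limit | 0.080 | 15.8 points |

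The last row is the floor set by the 29 recipients. Doubling the controls gains about 4 points, and tripling them about 5.

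**Step 3: what moderate steering would do.** If the true ICU rate is p and ICU cases have w times the odds of being picked, the rate among selected controls is q = wp / (wp + 1 − p). With p = 0.40 and no treatment effect:

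- w = 1.25: q = 0.50/1.10 = 45.45%, spurious benefit 5.45 points
- w = 1.5: q = 0.60/1.20 = 50.0%, spurious benefit 10.0 points
- w = 2: q = 0.80/1.40 = 57.1%, spurious benefit 17.1 points

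The plan names no test for this comparison, so an unpaired two-sided z-test at 0.05 with 29 per group is assumed. The chance of a false significant benefit is Φ[(d − 1.96 × SE₀)/SE₁], where d = q − p, SE₀ is the pooled and SE₁ the unpooled standard error. For w = 1.5, (0.100 − 1.96 × 0.1307)/0.1300 = −1.20, which gives about 12%. The values for w = 1.25 and w = 2 are about 6% and 25%, against 2.5% with no steering.

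The result depends little on p. The spurious benefit is 4.4, 8.3 and 15.0 points at p = 0.25, and 5.6, 10.0 and 16.7 points at p = 0.50.

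**The case against.** The strongest reply is that the only powered decision in the plan does not use these controls. That stands. A reader might infer that the primary ICU test can be steered by picking charts. It cannot, because the rule compares recipients with a fixed 50%. The reply does not cover the comparison named in Section 2.3 and the Summary, and it does not cover 28-day mortality.

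Second, nothing says that outcomes will be consulted or who selects. That also stands: the plan omits a safeguard, and does not describe cherry-picking. A reader might work out the extremes. With two eligible charts per recipient and a true rate of 30%, picking wholly on outcome could give a control rate anywhere from 0.30² = 9% to 1 − 0.70² = 51%. With three charts the range is 3% to 66%. Those ranges need every pick for all 29 recipients to be made on outcome, and the number of charts per recipient is not in the documents. They do not measure the likely bias.

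Third, a reader might infer that eligible controls will be thrown away. The documents give no pool size. At one centre, after the Section 4.3 filters, there may be little more than one match per recipient, and then both the discretion and the lost precision are small. One-to-one matching is also conventional, and the gain from more controls is modest because 29 recipients set the floor.

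Finally, age and sex are not the only filter, since Section 4.3 applies first. That is correct, but those criteria define who may be chosen and not which eligible patient is taken.

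**Conclusion.** The point holds for the comparison with controls and not for the powered test. Section 7.1 fixes 29 matched controls without a selection rule or an outcome-blind lock, so the control ICU and mortality rates could depend on which eligible charts were taken, and the plan could not show otherwise. The consequence is greatest for 28-day mortality.

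The size cannot be derived from the documents. The illustration of about 5 to 17 points of spurious benefit rests on an assumed 40% ICU rate and assumed selection odds of 1.25 to 2. The precision cost arises only if more than 29 eligible controls exist. It is then about 4 to 5 points of half-width with 58 to 87 controls, and cannot exceed about 8 points (24.1 − 15.8). Precision alone would not justify a change. Unprotected selection does, and the remedy is a cheap improvement.

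**What to change.** In Section 7.1, state a control admission window with a start and an end date. This means reconciling Section 3.2 (treated before the trial began) with Section 4.3 (admitted from 30 March 2020, no end date). Then use every admission in that window that meets Section 4.3 as the comparator, adjusted or standardised to the recipients' age and sex. This leaves no choice among eligible patients. The cost is abstraction of more charts. Adjustment for age and sex alone does not deal with differences in severity, which is a separate question.

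If one-to-one matching is kept, match by script on an extract that holds only admission variables and the Section 4.3 eligibility fields. Those fields must include plasma receipt and participation in other trials, because both can occur after admission. Fix the tie-break in advance, for example nearest admission date and then a seeded random draw. Freeze the matched list before ICU and mortality fields are abstracted. The cost is a separate extract, a short script and abstraction in two stages.

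Under either option, judge the fluid-risk exclusion before outcome fields are read.

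### Chart-review controls are matched on sex and age only, so a difference in baseline oxygen need or severity could pass for a plasma effect on ICU transfer or mortality

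*Combined protocol and SAP*

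**What the plan says.** The trial is single arm, and its outcomes are to be compared with hospitalised patients identified by chart review (1.0 Summary; 2.3 Study Design). The primary endpoints are ICU transfer and 28-day mortality (7.3.1).

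- **Matching.** Section 7.1: "The historic control group will consist of 29 patients who are gender and age (within 5 years) matched". No other factor is named.
- **Formal rule.** Section 7.1, repeated in 9.1: "reject ICU admission rate=50% if only 8 or less patients are admitted to ICU among 29 evaluable patients". The controls do not enter this rule.
- **Baseline data.** The Summary, under Assessment and Data Acquisition, lists "vital signs including temperature, respiratory rate, oxygen saturation, oxygen requirement", together with APACHE and SOFA, and describes both scores as measures of severity or mortality risk. Relevant data for the clinical controls are to come from charts.
- **Ceiling.** Ventilated patients and those above 6 L/min by nasal cannula are excluded as recipients (4.2) and as controls (4.3). For controls the test applies on admission.
- **Timing.** Recipients may enter up to 72 hours after admission (4.1) and are removed if they pass the ceiling before infusion (5.2.6). No counterpart exists for controls.
- **Adjustment.** Section 9.1 says analyses will be adjusted for covariates and gives age and co-morbid conditions as examples. The sentence follows the immune-biomarker regressions and the comparison with immunologic controls. Categorical clinical endpoints are to be summarised as counts and percentages.

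**The concern.** In a non-randomised comparison, the groups must be alike in whatever predicts the outcome. The documents do not say outright that oxygen need predicts ICU transfer, but the inference is safe: they use it as the threshold that bars or removes a patient, and they describe SOFA and APACHE as prognostic. Two people of the same sex and similar age, one on room air and one on 6 L/min, would be an acceptable matched pair under 7.1.

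The timing rules add a likely direction. A patient who worsens between admission and the planned infusion drops out of the treated group. The same patient in the control pool passes the admission screen, stays in, and may count as an ICU transfer. Matching on age and sex cannot correct that.

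At stake is whether a lower ICU or death rate among recipients than among controls can be attributed to plasma at all.

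**Working it through.** **1. The plan's own figure.** Inputs from 7.1: null rate 50%, target 25%, two-sided 0.05, power 80%. One-sample normal approximation:

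n = [(1.960 × √(0.5 × 0.5) + 0.842 × √(0.25 × 0.75)) / 0.25]² = [(0.980 + 0.364) / 0.25]² = 28.92, rounded up to 29.

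Power at n = 29 is 80.1% by the same approximation, so the stated figure reproduces. Taken exactly, the printed rule has P(X ≤ 8 | 29, 0.50) = 1.2% and P(X ≤ 8 | 29, 0.25) = 71.3%. That shortfall in exact power is a separate matter. The 1.2% is the reference value for what follows.

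**2. From case mix to ICU rate.** The documents give no ICU rate by oxygen need or severity, so these inputs are assumptions. Take two severity strata, plasma without effect, and controls split 50:50 with a true ICU rate of 50%, the plan's benchmark. If a share s of recipients is in the milder stratum:

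recipient rate q = s × (milder risk) + (1 − s) × (sicker risk).

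With risks of 30% and 70% and s = 60%: 0.6 × 30 + 0.4 × 70 = 46%. With s = 80%: 0.8 × 30 + 0.2 × 70 = 38%. A shift of 10 to 30 points in mix, times a 40-point risk gap, gives a spurious difference of 4 to 12 points, or 16% to 48% of the 25-point target (4/25 and 12/25).

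**3. From ICU rate to a false claim of benefit.** For the fixed rule, P(X ≤ 8 | 29, q) is the sum over k = 0 to 8 of C(29, k) q^k (1 − q)^(29 − k). The plan names no test against the controls, so the last column assumes an unpaired pooled z-test of 29 v 29 and counts only results favouring plasma (z > 1.96).

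| Stratum risks | Recipients in milder stratum | Recipient rate | Fixed rule met | 29 v 29 test favours plasma |
|---|---|---|---|---|
| any pair below | 50% (balanced) | 50% | 1.2% | 2.4% |
| 40% / 60% | 60% | 48% | 2.1% | 3.4% |
| 40% / 60% | 80% | 44% | 5.3% | 6.4% |
| 30% / 70% | 60% | 46% | 3.4% | 4.7% |
| 30% / 70% | 70% | 42% | 8.1% | 8.5% |
| 30% / 70% | 80% | 38% | 16.8% | 14.3% |
| 20% / 80% | 60% | 44% | 5.3% | 6.4% |
| 20% / 80% | 80% | 32% | 38.7% | 27.5% |

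The lower tail of a two-sided 0.05 test allows 2.5%.

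**4. How much adjustment the data can carry.** Expected ICU events at the planned rates: 29 × 0.50 = 14.5 controls and 29 × 0.25 = 7.25 recipients, about 22 in all. That supports one severity covariate, not several.

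**The case against.** The strongest reply is that the matched controls carry no formal decision. The only stated test compares recipients with a fixed 50%, and better matching would leave it unchanged. This stands, and a reader might wrongly infer that severity matching would protect the primary test. It would not. But the reply does not dispose of the point: the control comparison is part of the stated design, and the fixed test has the same weakness, because 50% is a fair null only for patients of matching severity.

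Second, severity is not ignored. The shared ceiling, floor-bed admission and common exclusions remove gross differences. Nor does the eligibility of patients with cancer, transplant or immunodeficiency show an imbalance, since 4.3 does not exclude them from the controls. What remains is the range from room air to 6 L/min, and timing.

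Third, the adjustment sentence in 9.1 is open-ended, and ICU admission is among the outcomes of the models it follows. Its scope is arguable. On the natural reading it governs the biomarker models, and it names no severity measure on any reading.

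A reader might also infer that a confidence interval for the control comparison will be too narrow. No such interval is planned, and leaving out a confounder is chiefly a matter of bias.

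Finally, this is a phase II trial of preliminary efficacy, and SOFA may be incompletely charted for floor patients. Both are fair, and both argue for a modest fix.

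**Conclusion.** The point holds as a limitation of the control comparison that should be corrected. Nothing in the plan balances oxygen need or severity below the shared ceiling, and the entry rules are applied at different times in the two groups. A favourable difference in ICU transfer or mortality could therefore reflect case mix. The timing rules make a bias towards plasma more likely than one against it, but the documents do not show that recipients will in fact be milder, and a reader should not infer that they will.

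The size is unknown. Under the assumptions shown, with no plasma effect, the chance of meeting the 8-of-29 rule rises from 1.2% at an untreated rate of 50% to 3.4% at 46% and 16.8% at 38%. These figures rest on assumed stratum risks and mix shifts, on a true control rate of 50%, and, for the two-group column, on a test that the plan does not specify. They illustrate sensitivity and are not estimates of the bias in this trial.

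**What to change.** Amend 7.1 and 9.1 before control outcomes are extracted:

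1. **Align time zero.** A control qualifies as a match only if, at the recipient's time from admission to infusion, that control was still in a non-ICU bed and within the ceiling. Count ICU transfer and 28-day mortality from that point in both groups.
2. **Use oxygen requirement at time zero.** Add it to sex and age as a matching factor in a few coarse categories, widening the age caliper where no match exists. Alternatively, make it the single pre-specified covariate in the comparison with controls.
3. **Keep SOFA for a sensitivity analysis**, where it is charted. About 22 events will not support a rich propensity score or several covariates on top of fine strata.
4. **Report both results.** Give the severity-matched or adjusted comparison beside the fixed-50% test, and state that the 50% benchmark is interpretable only if it fits the recipients' severity mix.
5. **Clarify 9.1.** Say which analyses the covariate sentence covers.

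The cost is SAP wording, slightly more chart review and analysis, and possibly some looser age matches. The size of the control pool is not stated, so whether close matches can be found should be checked first, without looking at outcomes.
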